# I. Purpose, Background and Rationale A. Aim and Hypotheses

### I. ABSTRACT

Fibromyalgia can be thought of as a centralized pain state where pain is manifested and experienced in different body regions at different times. Individuals with centralized pain feel more pain than would be normally expected based on the level of nociceptive input. Music has previously been shown to have a positive effect on pain, anxiety, and depression in chronic pain patients. However, the impact of music listening on objective measures of pain sensitivity in patients with chronic pain have not yet been described. The goal of this pilot study is to begin to understand the possible analgesic effects of music listening on objective measures of pain sensitivity in patients with fibromyalgia. Previous studies in patients with FM have shown that patients have reduced self-reported pain, increased mobility, and activation of the descending pain modulatory system in the brain after even a short, 5 to10-minute music listening intervention. Our proposed study will be the first to investigate whether objectively measured pain sensitivity is reduced by music listening in these patients.

This two-arm parallel randomized controlled pilot study will enroll 40 patients with fibromyalgia. Patients' pain thresholds and sensitivity will be measured using a battery of quantitative sensory tests (QST). All patients will have two testing sessions: one under testing as usual conditions with no-sound, and one while listening to either instrumental Classical music, selected by the researchers with careful consideration of the musical characteristics, or a nature sound placebo control condition. This careful experimental design will allow us to test whether music listening elicits greater analgesic effects over simple auditory distraction. To minimize potential bias we will employ sound cancelling headphones and randomization of conditions so that the researcher collecting the QST measures will be blinded to whether the patient is hearing music, nature sounds, or nothing. The proposed study is significant as it will identify whether music listening has an analgesic effect during pain threshold and tolerance testing for patients with FM that supersedes any effect of auditory distraction. Results from the proposed study may provide objective evidence that music listening objectively improves analgesia and pain management and thus could be considered therapeutic during situations where acute pain is expected

#### II. SPECIFIC AIMS

Aim 1: Determine whether music listening during pain sensitivity testing has an analgesic effect on pain thresholds and tolerance and whether this effect is of greater magnitude in comparison to a non-musical auditory stimulus in patients with Fibromyalgia (FM). In order to accomplish this

Aim, patients with FM will undergo a variety of quantitative sensory testing (QST) procedures in order to KUMC – HRPP- 03/12/2015 Page 1 of 19 fully characterize their peripheral and central nervous system pain processing systems, including mechanical pain sensitivity and temporal summation. QST testing will be done at baseline (no auditory stimulus of any kind) and then will be repeated within the same subject while listening to the auditory stimulus. Patients will be randomized to either the Music arm or the Placebo (nature sounds) arm. Half of the patients will listen to music, and half will listen to nature sounds during testing. Hypothesis 1a: We hypothesize that both listening conditions will reduce pain sensitivity (lead to higher pain thresholds and tolerance) as compared to the no-sound control. Hypothesis 1b: We hypothesize that the use of music listening during QST tasks will reduce pain sensitivity as compared to the use of only nature sounds. Aim 2: Identify whether the objective analgesic effects of music listening are associated with subjective measures of anxiety, pain catastrophizing, resilience, and measures of music experience and enjoyment. In order to accomplish this Aim, the degree of analgesic effect of auditory listening (as measured by the difference in QST measures between baseline and music listening) will be calculated and correlated to subjective measures of pain and other pain-related patient characteristics using patient-reported outcome (PRO) measures. Hypothesis 2: We hypothesize that greater analgesic effect of music listening will be associated with lower levels of anxiety, depression, and with higher levels of music experience and enjoyment.

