## II. Research Plan and Design

Overall Study Design. For Aims 1 and 2, we will enroll 40 patients with FM to undergo QST testing on two separate days: baseline (Testing As Usual, no sound) and auditory listening. Participants will be randomized to two auditory listening conditions: music listening and nature sound listening. The conditions will be counterbalanced across subjects such that some will have listening on their first testing day and no sound on the second, and the rest of the subjects will have no sounds on the first day and listening on the second. Participants will be seated in a quiet room and a heart monitor will be attached. The participant will wear headphones during all testing sessions (including the no-sound control). They will listen to 10 minutes of the specified auditory recording (or silence) prior to QST testing. The researcher will then conduct the QST while the participant continues to listen to the auditory recording. The study visit will last for approximately 1 hour. The researcher collecting QST data will be blinded to which recording the participant is hearing.

After screening, informed eConsent (paper consent forms will be available if requested), and enrollment into the study, all subjects will undergo an evaluation which includes a battery of questionnaires for patient phenotyping that will assess symptoms including pain, physical function, depression, anxiety, and catastrophizing symptoms. QST parameters will also be performed after questionnaire administration as described above.

Patient Population. Recruitment: Participants will be recruited from the KUMC [name], Comprehensive Spine and Pain Management Center's chronic pain clinics and surgical spine clinics. The Frontiers Registry and the Pioneers Community Research Recruitment Registry services through the Frontiers: The Heartland Institute for Clinical and Translational Research will also be used to foster the recruitment of participants from the community. We will also be using web-based recruitment pathways including Craig's List, social media, and the KUMC intranet. Patients will be paid for their time for all visits.

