#### Study Procedures / Outcome Measures.

Patient Characteristics Related to Pain and Music: This battery of questionnaires is intended to understand key aspects of pain, mood, and function as quickly and efficiently as possible.

 Demographics: Sex, age, race/ethnicity, marital status, education level, and body mass index (BMI) will be assessed in the context of standardized case report forms. Sex is an important biologic variable to investigate as centralized pain is more common in females, and is probably largely responsible for the fact that nearly any chronic pain condition is 1.5 – 2 times more common in women than in men.

- Medication List: A list of the medications participants are taking for pain and medications that may impact heart rate or pain sensitivity (i.e. opioid or analgesic medications).
- Fibromyalgia-ness (FMness): FMness is a measure of pain and co-morbid symptom extensiveness and severity. It is calculated by combining the scores from the Widespread Pain Index with the Symptom Severity Scale from the 2011 FM Survey to derive a continuous metric purportedly indicative of the degree of CNS pain amplification present in a given individual.
- Fibromyalgia Functional Status: We will assess the current health and functional status in FM patients using the Revised Fibromyalgia Impact Questionnaire (FIQ-R). The FIQ-R measures physical functioning, work status, and overall well-being.
- Clinical Pain Severity: Pain severity and functional interference due to pain will be assessed using the Brief Pain Inventory (BPI). The BPI is validated for chronic, non-malignant forms of pain, and asks patients to rate their current pain intensity, as well as their worst, least and average pain in the 7 days (0-10 NRS) and has been recommended by IMMPACT as a measure of choice for the assessment of pain in clinical research.
- Depression and Anxiety: To avoid patient burden with the multiple domains, this study will take advantage of the static short forms developed by the NIH roadmap initiative PROMIS. The PROMIS short forms will be used for Depression and Anxiety.
- Catastrophizing: Catastrophizing is associated with worse pain and the progression of chronic pain will be 6-item catastrophizing scale from the Coping Strategies Questionnaire(CSQ-CAT).

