## C. Sample size, statistical methods, and power calculation

Statistical Analysis: Data analysis will be performed by the KUMC Department of Biostatistics. The data analyst will also be blinded to whether data was during the nature sounds or music listening condition. Once all data have been collected and summary scores have been calculated, the database will be locked. Only then will the blind be broken for whether the QST scores were associated with music or nature sounds, and the final statistical test will be conducted.

Aim 1 Analyses: Pain thresholds and temporal summation scores will be treated as continuous measures and normality will be assessed prior to analysis. QST data will be analyzed using a paired t-test or appropriate nonparametric test to detect changes within-subject changes in QST measures between nature sounds or music listening.

Aim 2 Analyses: Magnitude of changes in QST measures between nature sounds and music listening will be calculated and correlated to the subjective measures of pain and music that are administered via patient-reported outcome questionnaires. All measures will be treated as continuous measures and normality will be assessed prior to analysis. These relationships will be analyzed using Pearson's correlation testing.

Sample size for Study Procedures in Aims 1 and 2: It is not possible to conduct adequate power analyses for the aims as this pilot study will be the first to measure QST changes with a music listening intervention in this patient population. Sample sizes for studies included in previous meta-analyses ranged from 25 to 175. We will use the data collected in this pilot study to estimate effect sizes for the next application for a larger trial.

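### Aim 2 promises an association with resilience, but no resilience measure is in the questionnaire battery

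*Combined protocol and SAP*

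**What the plan says.** The plan describes the Aim 2 measures in four places.

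- **Aim 2 statement (Specific Aims):** the effect is to be related to "subjective measures of anxiety, pain catastrophizing, resilience, and measures of music experience and enjoyment".
- **Next sentence of Aim 2:** the change in QST is to be "correlated to subjective measures of pain and other pain-related patient characteristics using patient-reported outcome (PRO) measures".
- **Hypothesis 2:** a greater effect is expected with "lower levels of anxiety, depression, and with higher levels of music experience and enjoyment".
- **Aim 2 Analyses (section C, sample size and statistical methods):** the change is to be "correlated to the subjective measures of pain and music that are administered via patient-reported outcome questionnaires", using Pearson correlation.

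The data to be collected are described in Study Procedures / Outcome Measures and again in section E (specific methods). Both copies list demographics, medications, FMness, FIQ-R, BPI, PROMIS depression and anxiety, the CSQ catastrophizing scale, the Brief MEQ with familiarity and liking ratings, and the Kirby delay discounting task. On mood, for example, both state: "The PROMIS short forms will be used for Depression and Anxiety". The overall design description, repeated in section B (Study Type and Design), says that the battery will "assess symptoms including pain, physical function, depression, anxiety, and catastrophizing symptoms".

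**The concern.** An aim can be answered only if the construct it names is measured. Resilience is named in Aim 2, yet nothing in the data collection plan would produce a resilience score. If this is noticed only at analysis, the trial must either stay silent on a stated aim or use another scale as a stand-in after the fact. The plan designates no stand-in. Catastrophizing cannot serve by default, because Aim 2 lists it as a separate construct.

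A lesser issue sits beside this. The aim, the hypothesis and the analysis text describe the measures differently, and the analysis text names no scale. The scales to be correlated are therefore left open for constructs that are measured.

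**Working it through.** The plan gives no figure for this point, so the check is a comparison of texts.

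**Step 1. Match each construct to an instrument.**

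| Construct | Aim 2 statement | Hypothesis 2 | Instrument in both copies of the battery |
|---|---|---|---|
| Anxiety | yes | yes | PROMIS short form |
| Pain catastrophizing | yes | no | CSQ-CAT |
| Resilience | yes | no | none |
| Music experience | yes | yes | Brief MEQ |
| Music enjoyment | yes | yes | liking rating after each session |
| Depression | no | yes | PROMIS short form |

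The Aim 2 statement names five constructs and four have an instrument, so 5 − 4 = 1 has none. Hypothesis 2 names four constructs and all four have an instrument.

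**Step 2. Could the gap come from text lost in extraction?** This is unlikely. The two copies of the battery agree item by item. In both, catastrophizing is followed directly by music experience, and the list ends with the Kirby task. The design summaries do not mention resilience either. The battery's questionnaires carry citations, and no title in the reference list names a resilience instrument.

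**Step 3. What does the analysis text cover?** Its category of pain and music measures closely follows the heading of the battery, Patient Characteristics Related to Pain and Music. The PROMIS scales, CSQ-CAT and Brief MEQ all sit under that heading. The operational sentence in Aim 2 also reaches beyond pain to other pain-related characteristics. Read this way, the text covers all the collected scales without naming any of them. It cannot cover resilience, which is not collected.

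**Step 4. How much room does the unnamed list leave?** This is an illustration under assumptions that are not in the plan: four QST outcomes (threshold, tolerance, PAIN50, wind-up ratio), one score per scale, independent tests and a two-sided level of 0.05. The plan states no level or multiplicity rule for Aim 2. The chance of at least one false positive among k tests is 1 − 0.95^k.

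- Hypothesis 2 constructs only: 4 × 4 = 16 tests, and 1 − 0.95^16 ≈ 0.56.
- Eight collected scores (BPI, FIQ-R, FMness, PROMIS anxiety, PROMIS depression, CSQ-CAT, Brief MEQ, liking): 8 × 4 = 32 tests, and 1 − 0.95^32 ≈ 0.81.

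Positive correlation among scales and outcomes would lower both figures. They show that the choice of list matters. They also show that agreeing on a list does not by itself control multiplicity.

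**The case against.** The strongest reply is that this is one stray word in an aim statement. No hypothesis depends on resilience, Aim 1 is untouched, and the study is a pilot meant to yield effect sizes, so exploratory correlation is its declared purpose. A directional hypothesis also need not repeat every construct in a broader aim. Most of this stands, and it limits the point. It does not remove it: resilience is still a stated object of Aim 2 with no data behind it, and exploratory status does not supply a measurement.

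A reader might go further and infer that the stated analysis does not test Hypothesis 2, because it speaks only of pain and music and not of mood. The documents do not support that. The wording follows the battery's own heading, under which the anxiety and depression scales are listed, and Aim 2 extends the correlations to other pain-related characteristics. Nor are there three contradictory lists: the analysis text is an unspecific category, not a competing list. What remains is loose specification of measures that will be available.

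**Conclusion.** The point holds for resilience: one of the five constructs in the Aim 2 statement cannot be addressed in any of the 40 patients as the plan stands. This rests on the two copies of the battery being complete, which their agreement supports.

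For anxiety, depression, catastrophizing, music experience and enjoyment the data will exist. The mismatch between aim, hypothesis and analysis text is a matter of naming scales, to be settled before the results are seen. It is not a failure to test Hypothesis 2.

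This conclusion concerns only which measures are correlated. The change score is also defined differently in the two places: baseline against listening in Aim 2, nature sounds against music in section C. That is a separate matter.

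**What to change.** **Main change.** Add a brief validated resilience scale, chosen by the investigators, to the REDCap battery and list it in both descriptions of the battery. The cost is a few minutes of patient time, and there would be no resilience data for anyone already tested. The documents do not show whether testing has begun. If the addition is no longer possible, remove resilience from Aim 2 so that the trial does not claim to address it. That costs only wording.

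**Secondary change, before database lock.** Name the same collected scales in Aim 2 and in the Aim 2 Analyses paragraph:

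- pain measures: BPI, FIQ-R and FMness, which must stay because both texts promise correlation with measures of pain;
- PROMIS anxiety and PROMIS depression;
- CSQ-CAT;
- Brief MEQ and the liking rating;
- the resilience scale, if added.

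Mark the Hypothesis 2 constructs (anxiety, depression, music experience, enjoyment) as pre-stated and all others as exploratory. This too costs only wording. It does not settle multiplicity, so the report should give all the correlations examined and present the exploratory ones as such.

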Music and sound delivery: Auditory stimuli will be presented using an iPod and Bluetooth noise-cancelling headphones. Listening will begin 10 minutes prior to QST and will continue for the duration of the QST, for a total of 1 hour and 10 minutes. The listening condition will be a single bout on one of two days of testing. This is a two-arm parallel design RCT with Testing as usual (no-sound) and placebo control (nature sounds).

Heart Monitoring: Subject's electrocardiogram (ECG) will be recorded with a measurement device (Biopac/AcqKnowledge software) that consists of a computer-operated recording device and amplifier. The recording device and amplifier are attached to standard snap-on ECG electrodes. Three ECG electrodes are placed: one under the collar bone, one under the rib cage on the opposite side, and a ground on the abdomen. ECG will be recorded throughout each testing session. The time of each condition (passive listening vs. active listening with sensory/pain stimulus) will be recorded by the investigator. The ECG will be uploaded to Kubios software for analysis. Metrics of heart rate and variability in time-, frequency, and non-linear domains will be compared between conditions (passive vs. active listening) and between sounds (nature sounds vs. music).

Music characteristics: The musical selections will be professional recordings of instrumental Classical music selected by the researcher (See Appendix 1). All participants will hear the same pieces in the same order. Instrumentation ranges from piano solo to full orchestra, but they are without lyrics or heavy percussion. Pitch ranges across the pieces, but is standard across participants and not controlled by either the participant or the researcher. Tempo for all of the pieces is slow (~60 beats per minute). The pieces are in either major keys or minor keys, but all consist primarily of consonant harmonies and sustained melodic phrases. Participants will control the volume to their individual comfort level.

Placebo control: Professional recordings of nature sounds selected by the researcher without added music will be used as the active placebo control condition. All participants will hear the same recording. This active control condition will allow for non-musical analgesic effects, such as distraction, to be controlled in the experimental design. Participants will control the volume to their individual comfort level.

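### Aim 2 has no analysis that could show an association specific to music: a trait that predicts response to any sound would look the same as a predictor of music analgesia

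*Combined protocol and SAP*

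**What the plan says.** **Design.** The Abstract states: "This two-arm parallel randomized controlled pilot study will enroll 40 patients with fibromyalgia". Each patient has a no-sound session; the other is "one while listening to either instrumental Classical music, selected by the researchers with careful consideration of the musical characteristics, or a nature sound placebo". The Specific Aims add: "Half of the patients will listen to music, and half will listen to nature sounds during testing". Under music and sound delivery: "The listening condition will be a single bout on one of two days of testing". Every patient therefore contributes silence and one sound, never both sounds.

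**Aim 2, Specific Aims.** The quantity is first called "the degree of analgesic effect of auditory listening" and is then defined in parentheses "as measured by the difference in QST measures between baseline and music listening". Hypothesis 2 is that "greater analgesic effect of music listening will be associated with lower levels of anxiety, depression, and with higher levels of music experience and enjoyment".

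**Aim 2, section II.C (statistical methods).** Here the change to be correlated is the one from nature sounds to music. The method is a single line: "These relationships will be analyzed using" Pearson's correlation. Neither section mentions an arm term, an arm-by-score interaction or a comparison of correlations between arms. Section II.C gives no alpha, target correlation or power. It says the data will supply effect sizes for a larger trial.

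**Purpose of the control.** The placebo control paragraph says the nature-sound arm is there so that effects of sound that are not musical, distraction among them, are controlled.

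**The concern.** A change from silence to music contains everything that differs between silence and any pleasant sound (distraction, expectation, general suggestibility) as well as anything particular to music. A questionnaire score that tracks the first part will correlate with the change in the music arm even if it has nothing to do with music. The trial has the arm needed to tell these apart, but no planned Aim 2 analysis uses it for that purpose.

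What is at stake is the wording of the conclusion and what is carried into the next trial. A general sound-responder trait could be reported, and designed around, as a predictor of response to music.

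**Working it through.** **1. Who has which score**

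| Arm | Patients | Silence to music | Nature sounds to music | Assigned sound minus silence |
|---|---|---|---|---|
| Music | 40/2 = 20 | yes | no | yes |
| Nature sounds | 40/2 = 20 | no | no | yes |
| Total | 40 | 20 | 0 | 40 |

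The score in section II.C cannot be computed for anyone. The parenthesis in the Specific Aims is the only explicit definition that can be computed, and only in the music arm. Assigned sound minus silence exists for everyone.

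**2. What a music-arm correlation measures**

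Write the change as S (response to any sound) plus, in the music arm, M (the additional part due to music) plus error. For a score X:

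- music arm: Cov(X, change) = Cov(X, S) + Cov(X, M)
- nature arm, as reference: Cov(X, change) = Cov(X, S)
- difference between arms: Cov(X, M)

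Only the difference, which is the arm-by-score interaction, isolates the music-specific part. A music-arm Pearson correlation tests the sum.

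**3. Size, by simulation**

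The plan has no figure of its own to reproduce. All settings here are assumptions: two-sided alpha 0.05, 20 per arm, no dropout, normal data, score and change with variance 1 in each arm, no session-order effect, 10,000 runs per row. The common slope is from the model with arm and score but no interaction.

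| True r, music / nature | Music-arm Pearson p < 0.05 | Interaction p < 0.05 (n = 40) | Common slope p < 0.05 (n = 40) |
|---|---|---|---|
| 0.3 / 0.3 | 25.4% | 4.8% | 47.2% |
| 0.5 / 0.5 | 64.4% | 5.0% | 91.7% |
| 0.3 / 0 | 25.3% | 14.3% | 15.0% |
| 0.5 / 0 | 64.0% | 34.2% | 34.4% |

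The Monte Carlo standard error near 64% is √(0.64 × 0.36 / 10,000) = 0.5 percentage points. A separate set of 8,000 runs gave 25.6% and 65.1% for the music-arm test at r = 0.3 and 0.5. The music-arm column is the same whether or not the nature arm shows the association, so that test carries no information on specificity.

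**4. Check by Fisher z**

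- One correlation of 0.5, n = 20: atanh(0.5) × √17 − 1.96 = 0.549 × 4.123 − 1.96 = 0.305, power 62%.
- Common correlation of 0.5, n = 40: 0.549 × √37 − 1.96 = 1.381, power 92%.
- Difference, 0.5 against 0, 20 per arm: 0.549 / √(1/17 + 1/17) − 1.96 = 1.601 − 1.96 = −0.359, power 36%.
- Difference detectable with 80% power: (1.960 + 0.842) × √(2/17) = 0.961 on the z scale, that is r of about 0.74 in music against 0 in nature sounds.
- Interval for an observed r = 0.3 at n = 20: tanh(0.310 ± 1.96/√17) = −0.16 to 0.66.

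These agree with the simulation to within about two percentage points.

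**The case against.** **Hypothesis 2 claims no contrast with nature sounds.** It says only that a larger effect of music goes with certain scores. If the true music-arm correlation is 0.5, that statement is true, and 65% is power, not an error rate. This stands. A reader might infer from 65% against 5% that the plan has a 65% false-positive rate; the documents do not support that. The figures show that the test cannot distinguish two explanations.

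**Nothing says the music arm alone will be analysed.** This also stands. A reader might infer that the plan restricts Aim 2 to the music arm and leaves the nature arm unused. But the Specific Aims also speak of "the degree of analgesic effect of auditory listening", which could cover both arms, and section II.C names nature sounds explicitly. Nor can Aim 1 be held up as the contrast: section II.C describes it as a paired, within-subject test in much the same terms. The both-arm reading does not rescue Aim 2, however. A pooled Pearson correlation without an arm term still says nothing about specificity. If music were both better liked and more analgesic, the difference between arms alone would produce a correlation between liking and change.

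**The interaction is weak.** True. For r = 0.5 against 0 it has about 34% power, against about 65% for the music-arm correlation alone. A reader might infer that moving from 20 to 40 patients buys power for the music question. It does so only for an association common to both sounds (about 92% against 65% at r = 0.5).

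**This is a correlational aim in a pilot that disclaims power.** Fair, and it limits the weight of the point. It does not justify a conclusion about music that the analysis cannot support.

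**Conclusion.** The point holds in this form: under either description of the change score, and under a both-arm reading, Aim 2 plans no analysis that could show an association specific to music. On the one explicit definition that can be computed, about 20 of 40 patients contribute.

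If a trait predicts response to any sound equally, the music-arm test is significant in about 25% of trials at r = 0.3 and 65% at r = 0.5, and the interaction in about 5%. The correlations, alpha, full retention and normality are assumptions; the counts and the absence of a between-arm analysis come from the documents. The consequence is a risk of over-interpretation, not a false result for Hypothesis 2 as worded. The change is worth making because it is cheap and uses data that will be collected anyway.

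**What to change.** 1. Define one change score for Aim 2, assigned sound minus no sound, for all 40 patients, and use that definition in both the Specific Aims and section II.C.
2. For each questionnaire score, regress the change on arm, score, arm × score and session order (listening on the first or second day, since days are counterbalanced).
3. Report the slope in each arm with its 95% confidence interval. The music-arm slope addresses Hypothesis 2 as worded.
4. Report the interaction with its 95% confidence interval as the only evidence of music specificity, labelled exploratory.
5. Take the common slope, the association with listening in general, from the model without the interaction. With 0/1 arm coding, the score coefficient in the interaction model is only the reference arm's slope.
6. Analyse liking and familiarity separately by arm. They are given after each session about different stimuli, so they are post-randomisation ratings and not baseline moderators.
7. Word the Aim 2 conclusion to match: an association within the music arm, an association with listening in general, or a difference between sounds.

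The cost is a few sentences and a few lines of code, with no new data or visits. The downside is the imprecise interaction; its interval will be wide and a non-significant result must not be read as absence of specificity.
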